### **14.1 Data Management Responsibilities**

The responsibilities designated to each member of the research team are documented on the Delegation of Authority SOP (*Appendix K*). The study coordinator and research assistants will be responsible for the informed consent process, review for eligibility, questionnaire administration, data entry, device administration, EEG administration, and CRF entries. The study coordinator will be responsible for AE/SAE documentation and reporting, while the PI will be responsible for the AE assessment, review of the AE documentation forms and overview of the research staff. [name] will be the medical monitor for the study.

### **14.2 Data Capture Methods**

Clinical data (including AEs, concomitant medications, and expected adverse reactions data) and clinical laboratory data will be entered into a data capture system provided by REDCap. The data system includes password protection and internal quality checks, such as automatic range checks, to identify data that appear inconsistent, incomplete, or inaccurate. Clinical data will be entered directly from the source documents.

### **14.3 Types of Data**

Data will be collected to determine eligibility. During the initial session, the SCID, AHRS, PANSS, CGI-S, SAS and AIMS will be administered. In order to participate in this study, the participant must have a diagnosis of schizophrenia or schizoaffective disorder, experience medication refractory auditory hallucinations, and are currently not committed in an inpatient hospital and on stable medication.

We will also be collecting data to assess cognitive abilities at the 1st day of stimulation, the 5th day of stimulation and end point (one month follow-up). The BACS will be used to assess cognition in each participant and will be used as a safety monitor and data collection tool to

monitor any changes throughout the course of the study.

The stimulation adverse effects questionnaire will be administered after each stimulation in order to monitor any side effects the participant may experience from the stimulation treatment. After the last stimulation and at the one week and one month follow-up, participants will be asked whether they believe their symptoms have improved due to treatment.

The AHRS will be our primary outcome for this study. We will administer this questionnaire at the initial session, on the 1st day of stimulation, the 5th day of stimulation, and the one week and one month follow up. As our primary outcome, the data we collect with the AHRS will be used to determine efficacy of treatment.

The PANSS, the CGI-S, the SAS and the AIMS will be used to collect additional data throughout the study. This questionnaire will also be administered on the 1st day of stimulation, the 5th day of stimulation, and the one week and one month follow up, in addition to during the initial session.

An EEG recording will be performed at the 1st day of stimulation, the 5th day of stimulation, and at the one week and one month follow-up. The data collected from the EEG recording will enable assessment of neurophysiological changes induced by stimulation.

#### **14.4 Timing/Reports.**

The stimulation adverse effects questionnaire will be administered at the end of each stimulation session and at each follow-up session. Any AE will be reported to the PI within 72 hours and to the medical monitor within 24 hours. Reports will be run at the end of each week and any unusual activity that could be a cause of concern will be reported to the PI at weekly meetings.

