## PROTOCOL SUMMARY

Title:	Targeting Auditory Hallucinations with Alternating Current Stimulation
Précis:	
The purpose to determine the efficacy of transcranial alternating current stimulation, tACS, versus sham stimulation (with tDCS versus sham as a positive control for assay sensitivity) for the treatment of medication-refractory auditory hallucinations in patients with schizophrenia. We will recruit 48 males and females diagnosed with schizophrenia or schizo-affective disorder. Eligible participants will have 5, twice-daily (one week Monday through Friday), 20 minute stimulation sessions. Stimulation will be at least 3 hours apart. Participants will be randomly assigned to one of three groups; sham stimulation, 10 Hz (alpha) tACS or 2 mA tDCS. Participation will involve 1 to 8 visits. At the initial session, informed consent will be obtained and subjects will be screened for eligibility. Eligible participants will then be scheduled for their, twice-daily stimulation sessions which will include daily assessment of stimulation side-effects. Clinical assessments will be performed at baseline, 1, 2 and 4 weeks using the Auditory Hallucinations Rating Scale (Attachment 3). Neurophysiological (EEG) and cognitive assays will be performed before and after stimulation. Please see Appendix A for a detailed schematic describing all visits and assessments.

Objectives:	
Our primary objective is to demonstrate the value of synchronization and information flow measures derived from EEG data as novel biomarkers in the treatment of medication refractory auditory hallucinations in schizophrenia with transcranial current stimulation. To reach this objective, we will test the working hypothesis that (1) baseline impairment in EEG synchronization and information flow predicts treatment success and (2) changes in these markers correlate with improvement of clinical symptom presentation as determined by the AHRS, PANSS, and BACS (Attachment 12). We will test our working hypothesis by measuring whole-head EEG data from all patients in our feasibility study (48 patients from Aim 1) before and

immediately after the five day course of stimulation and at both follow-up visits.

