## 7.3 Stimulation Sessions

### Day 1 of Stimulation (Visit 5)

At the first day of stimulation, vitals will be recorded and several questionnaires will be administered. First, the AHRS (*Attachment 3*) will be administered followed by the PANSS (*Attachment 5*) and the Brief Assessment of Cognition in Schizophrenia (BACS) (*Attachment 12*). The BACS will be used as a baseline assessment of participant cognition, and will be administered again during later sessions to assess for any changes in cognitive function associated with treatment. After this, the CGI-S (*Attachment 8*) will be administered in order to document any difference in auditory hallucination or symptom severity from the screening visit.

Once the questionnaires are complete, the participant will be administered either sham, 10 Hz tACS or 2 mA tDCS treatment for 20 minutes. Participants will be asked to sit still and not talk during these 20 minutes, and will be asked to keep their eyes open and facing straight ahead. After the 20 minutes of treatment, the participant will be asked to return 3 hours later on the same day for another 20 minutes of either sham, 10 Hz tACS or 2 mA tDCS treatment, where the participant will again be asked to sit still, not talk, and with their eyes open.

After each stimulation treatment, to assess any side effects of stimulation, the stimulation adverse effects questionnaire will be administered. This questionnaire will be administered at the end of each stimulation session as a safety assessment to monitor any potential side effects of the stimulation (*Attachment 1*). Participants will be paid at the conclusion of this session.

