## 9 ASSESSMENT OF SAFETY

### 9.1 Specification of Safety Parameters

There will be three different assessments used to ensure participant safety. First, vitals will be recorded at the beginning of each session. This assessment is used to monitor any physiological changes.

A Positive and Negative Syndrome Scale will be administered before the first stimulation session and on the last day of stimulation as well as at the one month follow up. This tool is used to assess any changes in symptoms associated with this disorder. We do not expect any changes in these symptoms; additionally we did not find any changes in a related clinical trial (IRB# 13-2995). Should there be a significant change in PANSS rating scores, (>25% increase) we will direct the participant to [name] or [name] for further follow up and file a AE report.

After each stimulation session, a stimulation adverse effects questionnaire (*Attachment 1* and *Attachment 2*) will be administered. This tool is used to document any side effects experienced during stimulation. The researcher will also check with the participant throughout the 20 minute stimulation sessions to make certain no discomfort is felt. The stimulation session will be terminated if the participant reports having unmanageable discomfort or pain (more than “moderate”). Additionally, this information will be reported on an AE report form (*Appendix B*) and an AE log (*Appendix C*).

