## 9.2.2 Expected Adverse Reactions

Transcranial current stimulation has been used without reports of any serious side-effects. Some subjects report a transient mild tingling, burning, or itching underneath the electrodes and headache, but no other side effects have been noted. Importantly, it remains unclear if these mild side effects were caused by the transcranial brain stimulation. During the stimulation, the researcher will ask the participant about their comfort. Stimulation will immediately be stopped if any discomfort (more than “moderate”) is reported. In theory, there is a possibility that application of weak stimulation current could induce a seizure.

These adverse reactions will be monitored with the stimulation adverse effects questionnaire (*Attachment 1 and Attachment 2*). The following scale reflects the scoring of severity for any possible side effects.

- 1 = Absence of the indicated symptom
- 2 = Mild (awareness of a symptom but the symptom is easily tolerated)
- 3 = Moderate (discomfort enough to cause the researcher to be informed)
- 4 = Severe (incapacitating; the stimulation is terminated due to extreme discomfort)

All expected adverse reactions questionnaires are a daily source document that will be placed in each individual’s folder. Should the DSMB ask to see a complete report of this information a report can be regenerated for their viewing.

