#### **9.2.4 Unanticipated Problems.**

Unexpected Events (UE) will be recorded on the UE/SAE log (*Appendix E*) and will include information such as the date of the event, when the study team was informed of this event, details of the event, when the IRB was notified, and whether the SAE Form was completed. The IRB will be notified of each UE that may occur during the study.

The Office for Human Research Protections considers unanticipated problems involving risks to participants or others to include, in general, any incident, experience, or outcome that meets all of the following criteria:

- Unexpected (in terms of nature, severity, or frequency) given (a) the research procedures that are described in the protocol-related documents, such as the IRB-approved research protocol and informed consent document; and (b) the characteristics of the participant population being studied;
- Related or possibly related to participation in the research
- Suggests that the research places participants or others at a greater risk of harm (including physical, psychological, economic, or social harm) than was previously known or recognized.

If an UE occurs the IRB will be notified and the study will be adjusted as needed to protect the health and safety of the participants. Depending on the nature of the UE, the research protocol, inclusion/exclusion criteria, and informed consent will be changed to reflect the possibility of this event reoccurring. *Please see Appendix F for an example of the Consent Amendment Tracking log.* During this time, no new participants will be recruited and the research procedures for currently enrolled participants will be stopped. Each UE will be recorded and reported throughout the study.

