## **9.6 Safety Oversight**

Safety oversight will be under the direction of a DSMB composed of [name], an epidemiologist, a biostatistician and one or more clinical researchers. The DSMB will review AEs every 6 months whereas the medical monitor will review AEs in real time and make decisions as to each participant's continuation in the trial. The PI will review AEs weekly with research team and may request additional review by Co-I on a case-by-case basis. The medical monitor will also be present at weekly meetings in order to discuss/explain any event(s) that may occur.

Every 6 months DSMB will review blinded AE reports. If there is reason to view unblinded information, the DSMB will directly receive the list of participants' identification numbers from a [name] Lab member, not otherwise associated with this clinical trial. Participant identification number will be displayed in a table according to the three arms of the study; however the specific treatment of that arm will not be disclosed. This will allow the DSMB to compare the three treatment groups.

Reasons for stopping the study and asking for further investigation include; decrease in cognitive abilities based on baseline and end of study data (>25% decrease in scores in 2/10 of the first participants or 20% of participants overall.). In addition, as mentioned above, if a seizure occurs during a study visit, the clinical trial will be temporarily be placed on hold for further investigation.

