## APPENDIX S: TELEPHONE RECRUITMENT SCRIPT

Hello, my name is \_\_\_\_\_. Are you contacting me in regards to the non-invasive brain stimulation study?

If 'No', redirect them as necessary)

(If 'Yes', proceed)

Do you have time now to hear about the study, answer a few screening questions, and schedule your first visit?

(If 'No', ask for a good time to call back)

(If 'Yes', proceed)

Great! This study is looking at how abnormal rhythms of brain activity in schizophrenia respond to very weak applied currents. Findings from this study will help the development of treatments for the symptoms of schizophrenia, like auditory hallucinations. In the study, a very weak current will be applied to your scalp. Some people report a mild tingling because of this stimulation, but no other side effects have been found. It is not a shock and should cause no pain.

Participation in this study includes one to eight sessions, with one session being an initial information session, then five, twice daily stimulation sessions, followed by a one week then one month follow up session. The stimulation sessions need to be on consecutive days with the second session occurring 3 hours after the completion of the first session. The maximum compensation for this study is \$340 for completing all of the sessions. Are you still interested in participating?

(If 'No', thank them for their time)

(If 'Yes', proceed)

Great! In order to make sure you're eligible for the study, I need to ask you a few questions. Please answer yes or no. You do not need to provide any further details.

(If the answer given is not the same as the answer shown, thank the individual for his or her interest and say unfortunately, they do not qualify for the current study)

- Are you 18 years old or older? (Yes)
- Have you ever, or are you currently being treated for a neurological condition (i.e. epilepsy)? (No)
- Are you currently taking any benzodiazepines or anticonvulsant medications? (No)
- Have you ever had brain surgery? (No)
- Do you have any brain devices or implants, including a cochlear implant or aneurysm clip? (No)
- Have you ever been diagnosed with a traumatic brain injury? (No)

- (For females only), Is there a chance you may be pregnant? (No)

Follow-up questions:

- Do you wear glasses/contact lenses?
  - Could you bring your contact lenses for the study visits instead of wearing your glasses?

(If answered according to all indicated responses, continue)

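### For an AE that ends a stimulation, 14.4 allows 24 hours to tell the medical monitor, while that participant's next stimulation can be due about 3 hours later

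*Combined protocol and SAP*

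**What the plan says.** **Reporting time.** Section 14.4: "Any AE will be reported to the PI within 72 hours and to the medical monitor within 24 hours". Two other AE time limits are also long: the PI initials the AE log 72 hours after it is completed (9.2.1), and clinical follow-up takes place within one week (9.4).

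**Who decides.** Section 9.6: "the medical monitor will review AEs in real time and make decisions" about whether each participant stays in the trial.

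**When the next stimulation is due.** Section 7.3, Day 1: "the participant will be asked to return 3 hours later on the same day for another 20 minutes". Appendix S describes the schedule "with the second session occurring 3 hours after the completion of the first session". The Protocol Summary sets a minimum and no maximum: "Stimulation will be at least 3 hours apart".

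**What ends a stimulation.** Section 9.1: "The stimulation session will be terminated if the participant reports having unmanageable discomfort or pain", with the threshold set above moderate, followed by an AE form and a log entry. The top score on the side-effect scale in 9.2.2 reads "4 = Severe (incapacitating; the stimulation is terminated due to extreme discomfort". Both rules concern the stimulation in progress.

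**What holds later stimulation.** A seizure at a study visit puts the study on temporary hold (9.5). After an unexpected event, 9.2.4 says: "During this time, no new participants will be recruited and the research procedures for currently enrolled participants will be stopped". Section 5.4.2 discontinues a participant after an AE when continuing would not be in that person's best interest.

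**The concern.** The monitor is named to decide on continuation, but the only stated time for telling the monitor is much longer than the gap between the two stimulations of a day. A first stimulation may be stopped because discomfort passed moderate. Staff could then give the second stimulation as scheduled, report that evening, and still be within the limit in 14.4. The participant would have been exposed again before the person responsible for the decision had heard of the event.

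What is at stake is participant safety and the consistency of 14.4 with 9.6. No analysis is at stake.

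**Working it through.** The plan gives no figure of its own for this comparison, so the check sets the gap between stimulations against the reporting limit.

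**Inputs**
- Stimulation length: 20 minutes (7.3). The 10-second ramps are ignored.
- Interval between the day's stimulations: 3 hours = 180 minutes (7.3, Appendix S).
- Schematic of Study Design: a 40-minute slot for each stimulation, a 1-minute questionnaire, then a 3-hour break.
- Limit for telling the monitor: 24 × 60 = 1,440 minutes (14.4).

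**Formula.** Let the AE stop the first stimulation at minute t, with t from 0 to 20. Let the second stimulation start at minute S, counted from the start of the first. Then gap = S − t, and the time left on the limit when the second stimulation starts = 1,440 − gap.

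| How the 3 hours are counted | S (min) | Gap (min) | Left on the limit (min) | 1,440 / gap |
|---|---|---|---|---|
| From the start of the first stimulation | 180 | 160 to 180 | 1,260 to 1,280 | 8.0 to 9.0 |
| From its planned end | 20 + 180 = 200 | 180 to 200 | 1,240 to 1,260 | 7.2 to 8.0 |
| From the actual stop | t + 180 | 180 | 1,260 | 8.0 |
| As a break after the slot and questionnaire, both slots laid out alike | 40 + 1 + 180 = 221 | 201 to 221 | 1,219 to 1,239 | 6.5 to 7.2 |

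Over all four readings the gap is 160 to 221 minutes. When the second stimulation starts, between 1,219 minutes (20 h 19 min) and 1,280 minutes (21 h 20 min) of the limit remain. The Protocol Summary's minimum lets the gap be longer, but 7.3 puts both stimulations on the same day, so it is always under 24 hours.

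**Do the hold rules close the gap?**
- Section 9.5 covers only a seizure at a visit.
- Section 9.2.4 could cover a stopped stimulation if the reaction were declared unexpected in severity. But all three of its criteria must be met, 9.2.2 places severe on the scale for expected reactions, and 9.3 sets times for reporting, not for classifying.
- Section 5.4.2 leaves discontinuation after an AE to judgement. It names no decision-maker, no deadline and no interim hold.
- Sections 9.1 and 9.2.2 are silent on the next stimulation.

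**The case against.** The strongest reply is that 14.4 sits in the data-handling section and sets an outer limit, whereas 9.6 is the operating rule. A prompt call satisfies both. A team that tells the monitor only after the next session could hardly claim to have given the real-time review that 9.6 describes. This stands in part: 9.6 shows a clear intention to act quickly. It still does not say that stimulation waits for the decision, and the only number attached to telling the monitor is 24 hours.

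Other safeguards also count:
- Section 5.4.2 allows discontinuation after an AE without waiting for the monitor.
- Trained staff attend every stimulation (6.2), comfort is checked during it, and the stop rule applies again next time.
- An approved clinician is present on stimulation day 5 for every participant, and on day 1 for the first five (Section 7).
- The participant may withdraw at any time.

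A reader might go further and infer any of the following, none of which the documents support:
- *Re-exposure before review is required or certain.* It is only permitted.
- *No hold rule exists anywhere.* Section 10.1 says that the approved IRB application governs conduct. That application and the reporting decision tree (Attachment 10) were not available, so the statement is limited to the available text.
- *Every later stimulation falls inside the 24 hours.* For an AE in the second stimulation of a day, this needs an assumption about the next day's start time, which the documents do not fix.
- *A ratio of 6.5 to 9 measures risk.* It compares an outer limit with a session gap. The documents give no rate for AEs that end a stimulation.

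**Conclusion.** The point holds in a limited form. For an AE that ends the first stimulation of a day, and is neither an in-visit seizure nor declared an unexpected event, the available text allows the second stimulation to be given before the monitor knows. The gap is 160 to 221 minutes against a limit of 1,440. This assumes a 20-minute stimulation, the four readings of the 3 hours shown above, and no contrary rule in the material that was not available.

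Given the safeguards, the expected harm is repeat discomfort under observation, with immediate stopping. The priority is low, and no estimate or test changes.

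**What to change.** In 14.4, with a cross-reference in 9.6, state that after any AE that ends a stimulation (discomfort above moderate, or questionnaire score 4), the medical monitor is told and the continuation decision is recorded before that participant's next stimulation. All other AEs keep the 24-hour limit. The trigger should be the stop itself, because 9.2.1 and 9.2.2 define severe differently.

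The cost is one sentence, one cross-reference, and an earlier call to someone who must be told anyway. The downside is an occasional delayed session, which the 3-hour minimum already permits, or a missed session made up on the following Saturday under 6.3. The missed-session rules and the timing of the AHRS can stay as they are. The end-of-stimulation AHRS in particular should not be altered for this purpose, because it is part of the primary outcome (3.2.1).
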